Specifically, meaning is viewed as both an intermediary outcome, as well as a mediator of changes in these important psychosocial outcomes. Religious faith is not expected to directly impact psychosocial outcomes, but may moderate the intermediary outcome of meaning (see, for example, Nelson et al., 2002, indicating that religious faith does not provide a unique contribution to enhanced psychosocial outcomes after controlling for spirituality). This model also presumes that other factors will impact response to a meaning-based intervention, including prognostic awareness, psychosocial treatment preference, and therapeutic alliance. We recognize that the directionality of many of the variables included in this model could potentially be bi-directional; however, we are presenting the model we believe underlies the intervention.

Figure 2: Study Model – Mediators and Moderators of Treatment Outcome

Spiritual Well-Being/meaning and Its Impact on Psychosocial Outcomes in Advanced Cancer

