Spiritual Well-being							
FACIT Total	2.24	2.72	1.21	.0001	2.60	0.69	.0005
Meaning/Peace	2.49	2.98	1.01	.0001	2.78	0.53	.006
Faith	1.69	2.15	0.66	.0002	2.25	0.63	.002
Psychological Functioning							
Anxiety	2.39	2.24	0.22	.17	2.16	0.48	.02
Depression	2.09	1.98	0.22	.18	1.89	0.51	.07
Hopelessness	7.57	4.70	0.80	.0001	4.84	0.63	.002
Physical Functioning/QOL							
Overall Quality of Life	5.89	7.18	0.94	.0001	6.88	0.71	.0003
Number of Symptoms	18.7	16.0	0.32	.06	17.5	0.14	.42
Symptom Distress	1.95	1.53	0.79	.0001	1.84	0.22	.22

Note: *M* pre: group mean at baseline; *M* post: group mean at end of treatment; *M* F/U: group mean at 2-month follow-up assessment;
 d , p correspond to effect size for comparison to baseline score (*M* pre)

Table 1 reveals that the therapeutic benefits of IMCP were somewhat more modest at the 2-month follow-up, but remained strong and statistically significant for most variables. In fact, some variables demonstrated more substantial improvements at the follow-up assessment (i.e., anxiety and depression). No such changes were evident in the TM treatment arm, with the —null findings continuing at the 2-month follow-up assessment.

Conclusions: IMCP appears to be a potentially beneficial intervention for patients' emotional and spiritual suffering at the end of life. Participants who received IMCP demonstrated substantial

and statistically significant improvements in spiritual well-being, a sense of meaning, hopelessness, overall quality of life, and symptom-related distress, and more modest effects for anxiety, depression and symptom burden. These treatment gains were sustained at the follow-up assessment, 2 months after completion of treatment. Patients who received TM, on the other hand, demonstrated little improvement in these outcome variables. When comparing the effects of these two treatments, IMCP resulted in significantly greater improvements in a number of variables studied. Further research that compares IMCP with other psychotherapeutic interventions, such as this current larger randomized control trial and includes a non-active control group, is needed to better understand the unique benefits of this treatment approach.

Potential Advantages of IMCP for Advanced Cancer Patients

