1. FACIT Spiritual Well-Being Scale (FACIT-Sp): The FACIT Spiritual Well-Being Scale is a brief self-report measure designed to assess the nature and extent of individual's spiritual well-being (Brady et al., 1999, Peterman, Fitchett & Cella, 1996). This measure, which generates two sub-scales: Faith (the importance of faith/spirituality) and Meaning /Peace (sense of meaning and purpose in life) (range 0-4), has been demonstrated to have strong internal reliability for both the total score and each subscale (coefficient alpha = .87 for the total scale, .88 for the faith factor and .81 for the meaning factor). In addition, strong support for the external validity of this measure has been demonstrated in a several large samples of cancer and AIDS patients including patients with advanced and terminal illness (Brady et al., 1999, [name] et al., 2001; Nelson et al., 2002). (5 minutes; T1, T2, T3, T4)

Measures of Religiosity:

1. Intrinsic/Extrinsic Religiosity Scale (IE-12): The Age Universal I-E Scale is a 12 item self-report measure that assesses intrinsic and extrinsic religiosity (Maltby, 1999). Each item is anchored on a three point scale (range 0-2). Items on the intrinsic scale include —My whole approach to life is based on my religion, and —It is important to me to spend time in private thought and prayer. Extrinsic religiosity items include —I go to church because it helps me to make friends, and —Prayer is for peace and happiness, (Allport & Ross, 1967). The measure has adequate internal consistency reliability (alpha range = .66 to .75) and has been increasingly used with elderly and medically ill populations (e.g., Nelson, 2002). (under 5 minutes; T1)

Measures of Psychological Distress and Quality of Life:

1. Hospital Anxiety and Depression Scale (HADS): This is a 14 item self-rated questionnaire, which has been well tested as a measure of overall psychological distress in cancer populations (range 0-42), with Depression and Anxiety Subscales of seven items each (range 0-21). It is considered particularly useful because of the absence of somatic items that often confound the determination of psychiatric problems among the medically ill. Strong test-retest reliability has been found in samples of elderly patients (Spinoven et al., 1997) and HIV positive patients (Savard et al., 1998). (under 5 minutes; T1, T2, T3, T4)

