Output:	Noncentrality parameter λ	= 20.8000000
	Critical F	= 2.9936309
	Sample size	= 104
	Actual power	= 0.8062691
	Pillai V	= 0.1666667

A sample size of 104 per randomization arm (138 at baseline) at post-intervention would accommodate a post-intervention attrition rate of up to 25%, which is within the attrition rate in our pilot IMCP trial. The estimated sample size at the follow-up time point (week 15) is 90 participants per intervention condition.

Based on our current IMCP Group psychotherapy intervention, we are currently recruiting at a rate of 5 – 6 individuals to participate. This study involves the IMCP individual therapy, which is more flexible in terms of enrolling patients quickly and scheduling for starting of the therapy sessions. Thus we are confident that we will be able to recruit at a rate of 8 – 9 individuals per month and complete the total enrollment of 414 within the 4-year recruitment period.

Data analytic plans for the secondary aims

To examine clinical and demographic variables that may correspond to differential responses to Individual Meaning-Centered Psychotherapy (e.g., potential moderating influences such as gender, race/ethnicity, religiosity, level of pre-intervention social support, optimism, physical symptom burden, prognostic awareness, and treatment dose).

We anticipate that several socio-demographic and clinical variables will moderate the impact of IMCP. For example, we expect that level of religiosity (based on the IE-12) at the baseline/pre-intervention assessment will be inversely related to treatment response (i.e., less religious individuals will be more likely to experience benefits from this intervention than more religious individuals). We also predict that level of social support will moderate improvement, with those patients reporting higher levels of social support receiving the greatest benefits (because of the emphasis on connectedness to others as a source of meaning in the IMCP intervention). On the other hand, we expect that patients with poorer physical functioning (e.g., lower Karnofsky score), greater pain severity and overall symptom burden (MSAS Global Distress Index scores) will be less likely to benefit from the interventions, in part because unmanaged physical symptoms may impede participation.

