Analyses: Putative explanatory covariates will be identified and tested statistically using the method originally described by Baron and Kenny (1986), and more recently by MacKinnon (2008). Specifically, these will involve Multi-Variate Analysis of Covariance (MANCOVA) using the changes in the six primary outcomes (post intervention minus baseline) as a function of intervention condition, controlling as covariates the effects of gender, race/ethnicity, and baseline covariates in religiosity, social support, optimism, physical symptom burden, pain severity, and overall symptom burden. This analytic approach entails the following advantages: 1) change scores have the advantage of clearly identifiable direction of change, 2) psychosocial outcomes are measured on an interval scale (such as measures of temperature in the Fahrenheit or Celsius scales), so that change scores are less prone to problems associated with respondents using different internal psychological scales; and 3) precedence exists (Flay et al. 1995) in interventions designed for behavioral change. This method offers several advantages, both in terms of power as well as interpretation, to a traditional repeated measures design for analyzing data when both independent and dependent variables are assessed at two or more time points (Huck & McLean, 1975; Willet, 1988-9). Change score analyses will include the baseline score as a covariate if change is significantly correlated with baseline score (as is often the case).

To assess the relative impact of Individual Meaning-Centered Psychotherapy on different aspects of meaning (e.g., purpose, coherence, existential vacuum), as well as on different aspects of spiritual well-being (meaning versus faith):

Two additional MANOVA models will be carried out. In the first model, pre-post change scores of different aspects of meaning (e.g., purpose, coherence, existential vacuum) will be modeled by intervention conditions to examine the relative impact of IMCP on these outcomes. The canonical weights will be used to estimate the relative contribution of each mean components on the overall canonical function. Components of spiritual well-being will also be analyzed similarly, in a separate MANOVA model. Univariate ANOVA contrasts will be used to compare IMCP against ISP and IMCP against EUC.

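### The religiosity moderator analysis cannot separate moderation of meaning from moderation of faith: the FACIT-Sp total carries Faith at about one third weight, and no arm-by-religiosity term is written

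*Combined protocol and SAP*

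**What the plan says.** Section 3.0, in the conceptual model, treats meaning as the intermediary outcome and gives faith a possible moderating role on it: "Religious faith is not expected to directly impact psychosocial outcomes, but may moderate the intermediary outcome of meaning".

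Section 11.0, under the secondary aims, makes religiosity its first moderator prediction: "we expect that level of religiosity (based on the IE-12) at the baseline/pre-intervention assessment will be inversely related to treatment response". Treatment response is not tied to any one measure.

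The analysis that follows is a MANCOVA "using the changes in the six primary outcomes (post intervention minus baseline) as a function of intervention condition". Religiosity appears among the baseline covariates, and no arm-by-religiosity term is written. Sections 9.1 and 11.0 list FACIT-Sp as one of the six outcomes, beside LAP-R as the measure of meaning.

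Section 7.1 says that FACIT-Sp "generates two sub-scales: Faith (the importance of faith/spirituality) and Meaning /Peace (sense of meaning and purpose in life) (range 0-4"). Section 11.0 also plans a separate MANOVA of the spiritual well-being components, but by intervention arm and not by religiosity.

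**The concern.** The conceptual model asks whether faith alters how much meaning a patient gains. One of the outcomes that would answer this contains a Faith score. A patient's religiosity may well bear on how far the Faith items move during IMCP, whatever happens to meaning. A religiosity effect on the FACIT-Sp total could then come from the Faith items, the Meaning/Peace items or both, and the total cannot say which.

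At stake is the reading of a named secondary aim with a stated direction. An interaction on the total could be reported as showing who gains meaning from IMCP when only Faith differed. A real difference in meaning could also be hidden by an opposite difference in Faith. The absent interaction term comes first, but adding that term and keeping only the FACIT-Sp total would bring this ambiguity in.

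**Working it through.** **1. Weight of Faith in the total.** The inputs are the IMCP rows of Table 1 in Section 3.0: "FACIT Total 2.24 2.72 1.21 .0001 2.60 0.69 .0005"; "Meaning/Peace 2.49 2.98 1.01 .0001 2.78 0.53 .006"; "Faith 1.69 2.15 0.66 .0002 2.25 0.63 .002". Write Total = (1 − w) × Meaning/Peace + w × Faith, so w = (Meaning/Peace − Total) / (Meaning/Peace − Faith).

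- Baseline: (2.49 − 2.24) / (2.49 − 1.69) = 0.25 / 0.80 = 0.31
- Post-treatment: (2.98 − 2.72) / (2.98 − 2.15) = 0.26 / 0.83 = 0.31
- Follow-up: (2.78 − 2.60) / (2.78 − 2.25) = 0.18 / 0.53 = 0.34

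Setting w = 1/3 rebuilds the printed totals as 2.22, 2.70 and 2.60, against 2.24, 2.72 and 2.60. All are within 1%.

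**2. Faith moves under IMCP.** The pilot contrast with massage was b = 0.39 (p = .03) for Faith and b = 0.36 for Meaning/Peace (Section 3.0). Within IMCP, Faith rose by 2.15 − 1.69 = 0.46 and Meaning/Peace by 2.98 − 2.49 = 0.49. With w = 0.31, Faith supplies 0.31 × 0.46 = 0.14 of the total gain of 0.48, or about 30%.

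**3. What an interaction on the total measures.** Interaction on Total = (1 − w) × (meaning difference) + w × (Faith difference), each difference being between religiosity groups in the treatment effect.

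- With equal meaning gains, the result is w × (Faith difference), and its sign is the sign of the Faith difference.
- A true meaning difference is cancelled by an opposite Faith difference (1 − w)/w times as large: 0.69/0.31 = 2.2, or 2.0 at w = 1/3. For example, (2/3) × 0.30 − (1/3) × 0.60 = 0. In simulation that case is flagged 5% of the time on Total and 59% on Meaning/Peace.

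**4. Illustration for FACIT-Sp alone.** This is not the planned joint MANCOVA. Assumptions:

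- 104 per arm (Section 11.0), IMCP against one comparator, religiosity split into halves (four cells of 52), two-sided 5% level.
- SD of change = mean change / d, reading Table 1's d this way: Meaning/Peace 0.49/1.01 = 0.485; Faith 0.46/0.66 = 0.697.
- Uncorrelated changes. The SD of change in Total is then √[(0.69 × 0.485)² + (0.31 × 0.697)²] = 0.398. Table 1 gives 0.48/1.21 = 0.397, so its figures imply a correlation near zero.
- Equal meaning gains in both halves. The pilot Faith gain of 0.46 is split as 0.58 and 0.34, 0.69 and 0.23, or 0.92 and 0. These splits are assumed.

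The standard error of the interaction is 0.398 × √(4/52) = 0.110.

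| Faith-gain difference | Shift in Total (× 0.31) | Shift / SE | Flagged |
|---|---|---|---|
| 0.24 | 0.074 | 0.67 | about 10% |
| 0.46 | 0.143 | 1.29 | about 24% |
| 0.92 | 0.285 | 2.58 | about 72% |

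The flagged rates are from simulation. The closed-form t calculation with 204 degrees of freedom gives 10%, 25% and 73%. On Meaning/Peace the rate is the nominal 5%. The shifts are about 16%, 30% and 59% of the pilot gain of 0.48 in Total. Reversing the split gives the same rates with the opposite sign.

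**The case against.** The strongest reply has four parts.

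- **The illustrated test is not the planned one.** Section 11.0 fits six outcomes jointly. FACIT-Sp is one of them and its canonical weight is unknown. This stands. A reader might infer that the joint MANCOVA would be wrong at the rates above, but the documents do not support that. The rates describe FACIT-Sp only, and LAP-R, for which no faith subscale is described, sits in the same model.
- **Section 11.0 does not confine response to meaning.** Spiritual well-being is a primary outcome in its own right. If IMCP raises Faith more in one religiosity group, that is genuine moderation of the FACIT-Sp. This also stands. A reader might call such a result a false positive, but it is one only if it is reported as moderation of meaning.
- **The overlap is not quantified.** No correlation between IE-12 and the Faith subscale is given, so one cannot say that they measure the same construct. Nor is a ceiling shown, since pilot Faith means were 1.69 and 2.15 on a 0 to 4 scale. Both points stand. The arithmetic needs only that Faith gain may differ by religiosity.
- **The plan has safeguards.** Subscales are scored, individual outcomes may be analysed, and baseline is adjusted for when it correlates with change. An interaction may also be intended, since the section cites a methods paper on moderators and mediators. These help only in part. The component analysis is by arm alone and the interaction is not written. A baseline covariate does not remove a Faith-gain difference confined to the treated arm. With a continuous religiosity score the simulated rates were 7%, 17% and 55%, and with an added baseline covariate 8%, 17% and 52%.

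**Conclusion.** The point holds as a minor one. Faith carries about one third of the FACIT-Sp total (0.31 to 0.34), it responded to IMCP in the pilot, and no planned religiosity analysis separates it from Meaning/Peace. As written, Section 11.0 tests no moderation by religiosity at all. Once an interaction is added, a result on the FACIT-Sp total cannot be attributed to meaning.

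The size depends on how far Faith gain differs by religiosity, which the documents do not report. Over the assumed range of 0.24 to 0.92 the flagged rate on FACIT-Sp runs from about 10% to 72%. It also rests on reading d as mean change over SD of change, on uncorrelated changes, on the same SDs in both arms, and on no religiosity difference in Faith change in the comparator.

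A reader might also infer that a religiosity effect could disappear with no difference in meaning. It cannot, because masking needs a true meaning difference and an opposite Faith difference about twice as large. The primary MANOVA is not affected, and the model statement in Section 3.0 contains no error.

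**What to change.** In the moderator analysis of Section 11.0, for religiosity:

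- add an arm by IE-12 term to the model;
- test it on Meaning/Peace and LAP-R, named as the measures of meaning;
- report the same term for Faith separately;
- state that an interaction on the FACIT-Sp total will not be read as moderation of meaning.

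Keep the FACIT-Sp total in the primary MANOVA. The cost is a few lines of text, since the subscales are already needed for the meaning-versus-faith aim. The downsides are slightly lower reliability (alpha .81 for the meaning factor against .87 for the total, Section 7.1) and a few more secondary tests. The false discovery rate procedure that Section 11.0 already mentions could cover those tests.

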4.1 OVERVIEW OF STUDY DESIGN/INTERVENTION

4.2 Design

This study will utilize a randomized, controlled, repeated measures design to investigate the efficacy of Individual Meaning-Centered Psychotherapy (IMCP), compared to a standard Individual Supportive Psychotherapy (ISP) and an enhanced usual care (EUC) arm, on spiritual well-being, psychological distress, and quality of life in a sample of 414 ambulatory patients (138 per arm) with advanced cancer. All patients with solid tumors with advanced disease and significant distress who are receiving ambulatory care at MSKCC are eligible for participation. Recruitment of patients will take place at MSKCC, in all ambulatory care areas treating solid tumors (i.e., prostate, breast, lung, colorectal, hepatobiliary, head and neck cancers, and Palliative Medicine). In addition, patients may be recruited through letters.

Potential subjects for the study will be identified, by the research staff and participating oncology staff, by cancer diagnosis and prognostic indicators of advanced disease. Specific evidence of advanced disease to meet eligibility criteria includes documentation of one of the following: stage IV disease for breast, prostate, or colon cancers; solid tumor malignancies at other sites that are metastatic; locally advanced and unresectable cancer/tumors; locally recurrent ovarian cancer, or confirmation from the treating physician and documentation in the research medical record of advanced disease. The Screening Assessment (T0) will be conducted using the following: Patients will be assessed using the Karnofsky Performance Rating Scale (KPRS). Patients with a score below 60 or physical limitations sufficient to preclude participation will be excluded from the study. Potentially eligible patients will be administered the Distress Thermometer (DT), developed by the National Comprehensive Cancer Network (NCCN) Distress Management Clinical Practice Guidelines Panel (2009). This screening tool consists of a 0 to 10 visual analog scale in the form of a distress thermometer as well as a checklist of problem areas that may be contributing to distress (i.e., practical, family, emotional, spiritual/religious, and physical problems), in order to determine whether the patient meets the requisite threshold for study participation. Patients who indicate a four or greater on the DT will be informed of the nature of the study, the method, relevant risks and benefits, and offered participation. Demographic (age, race, education, SES, etc) and Health Status (cancer diagnosis, stage of disease), and pre-randomization preference (treatment preference) will also be collected (see Appendix A). Patients will then complete the informed consent.

Following informed consent, patients will be assigned a subject number and randomized to one of the two 7 session interventions (IMCP vs ISP) or to the EUC control condition. Randomization will be completed by MSKCC's Department of Biostatistics. After randomization, participants will be contacted and informed which randomization assignment they received and scheduled for the intervention. The intervention should begin within four weeks of randomization. Patients who cannot begin the intervention within 30 days of consent (because of conflict or illness), will be placed on a waitlist so they can be offered the intervention when they do not have any conflicts at which time patients will be re-consented.

After the patient has been randomized, they will complete a T1-Baseline Assessment (week 1) before the 1st session (see Appendix C). The assessment battery will be re-administered at 3 subsequent points: T2 (midpoint, at session 4, Appendix D); T3 (post-intervention, following the 7th session of the intervention or at the completion of 14 weeks, whichever occurs first, Appendix E) to assess changes over the course of treatment; and T4 (follow-up, 8-12 weeks post completion of T3, Appendix F) to assess maintenance of treatment gains. The EUC sample will also be administered the battery of questionnaires at approximately equivalent intervals. Please see Appendices A, C, D, E, & F and if it is overly burdensome to come to the counseling center for assessments patients will be given the option to complete them by mail, email the blank questionnaires to participants for them to print and complete at home (forms will be returned by mail), or administer the questionnaires over the phone. Figure 3, section 9.0 for specific measures)

All intervention sessions will be conducted at Ambulatory Counseling Center facilities of the MSKCC Department of Psychiatry and Behavioral Sciences or another Memorial Sloan-Kettering Cancer Center treatment facility. However, in rare circumstances if deemed appropriate by the interventionist (e.g., illness, emergency, transportation difficulties) telephone sessions will be permitted. All psychotherapy sessions will be audio recorded to be used for treatment integrity purposes. Portions of these audio recordings may be transcribed for academic, educational, or

training purposes with the participants consent. This will happen when a portion of a session is particularly compelling or represents a noteworthy example of Meaning-Centered Psychotherapy in practice. Transcription will be completed by research staff or Ubiquis, a transcription service company. Sessions may be observed with the participants' knowledge by trainees and/or study personnel through the two way mirror in the MSK Counseling Center for training, educational, supervision purposes or for treatment integrity. Finally, sessions may be video recorded with the participants consent and may be used for academic, educational, or training purposes.

We will be assisted on this project by [name] from the Fordham University Department of Psychology. [name] is a Professor and Director of Clinical Training at Fordham with a faculty appointment at MSKCC. As Co-PI on the R01 grant that was awarded to support operations of this study, his primary role is to provide consultation for research design, research supervision, data analyses, and manuscript preparation. There is an established subcontract between MSKCC and Fordham University. All data that [name] receives will be de-identified.

